6 HANDLING OF MISSING VALUES AND OTHER DATA CONVENTIONS

Patients with missing values at a particular time point will be unevaluable at that time point. Missing data will not be imputed.

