d. Tumor assessments will be conducted using CT or MRI at trial discontinuation or disease progression, whichever is later. All sites of disease must be followed using the same baseline assessment method.

e. CA19-9 assessments will be taken at baseline and approximately every 3 weeks during the trial treatment period and at the end of treatment visit. All CA19-9 assessments are to be assayed by the same laboratory for each patient. The Investigator is encouraged to obtain radiological assessments and CA19-9 values earlier if there is a strong clinical suspicion of disease progression, in order to confirm or refute the clinical impression.

f. Site to provide patient with Fecal Swab sample collection kit and instructions to collect sample at home within the 72 hours prior to the scheduled 30-day follow-up visit. Patient will return fecal sample to clinic during the scheduled visit, or make

arrangements to drop sample off within 72 hours of collection.

g. Adequate contraception as defined by the protocol should be used throughout the trial and for at least 120 days for males w/WOCBP sexual partner and 180 days for WOCBP from the last dose of trial treatment. Refer to Section 4.7.2. for complete details.

h. Site to confirm contact information for patient and a designated family member and remind patient of FU telephone contact that will be conducted every 90 days for survival status

i. During the Survival Follow-up Phase the patient should be contacted by telephone 90 ± 5 days from EOT and every 90 ± 15 days after that until death, withdrawal of consent, or the end of the trial, whichever occurs first.

j. For only those patients that consent to the optional tissue collection. (Refer to 6.1.2.8).

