8.3.4 Analysis of Primary Endpoint - Disease progression at 6 months

All patients that receive trial treatment will be included in the analysis to determine the percentage of patients progressing by RECIST 1.1 criteria at 6 months when maintained on a combination regimen of paricalcitol plus pembrolizumab versus pembrolizumab alone. The 6-month time-point will be defined as 6 months (180 days) from the initial treatment (cycle 1/day 1). Statistical analysis will compare the proportion progression free at 6 months using a one-sided test of binomial proportions (equivalent to a Pearson's chi-squared test). If the assumptions of the Pearson's chi-squared test are not met, we will analyze the data using Barnard's exact unconditional test of equality, as implemented in StatXact²⁰

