Complete Response (CR): disappearance of target and non-target lesions and normalization of tumour markers. Pathological lymph nodes must have short axis measures < 10 mm (Note: continue to record the measurement even if < 10 mm and considered CR). Residual lesions (other than nodes < 10 mm) thought to be non-malignant should be further investigated (by cytology specialized imaging or other techniques as appropriate for individual cases⁴ before CR can be accepted. Confirmation of response is only required in non-randomised studies.

Partial Response (PR): at least a 30% decrease in the sum of measures (longest diameter for tumour lesions and short axis measure for nodes) of target lesions, taking as reference the baseline sum of diameters. Non target lesions must be non-PD. Confirmation of response is only required in non-randomised studies.

Stable Disease (SD): Neither sufficient shrinkage to qualify for PR nor sufficient increase to qualify for PD taking as reference the smallest sum of diameters on study.

Progressive Disease (PD): at least a 20% increase in the sum of diameters of measured lesions taking as references the smallest sum of diameters recorded on study (including baseline) AND an absolute increase of ≥ 5 mm. Appearance of new

lesions will also constitute progressive disease (including lesions in previously unassessed areas). In exceptional circumstances, unequivocal progression of non-target disease may be accepted as evidence of disease progression, where the overall tumour burden has increased sufficiently to merit discontinuation of treatment or where the tumour burden appears to have increased by at least 73% in volume. Modest increases in the size of one or more non-target lesions are NOT considered unequivocal progression. If the evidence of PD is equivocal (target or non-target), treatment may continue until the next assessment, but if confirmed, the earlier date must be used.

Table S1: Integration of target, non-target and new lesions into response assessment

| Target Lesions | Non-Target Lesions | New Lesions | Overall Response | Best Response for this Category also Requires |
|---|---------------------------|-------------|------------------|--|
| Target lesions ± non target lesions | | | | |
| CR | CR | No | CR | Normalization of tumour markers, tumour nodes <10 mm |
| CR | Non-CR/Non-PD | No | PR | |
| CR | Not all evaluated | No | PR | |

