7 STATISTICAL METHODOLOGY

7.1 STATISTICAL PROCEDURES

Primary outcome: Progression-free survival

The proportion of patients in each arm who are progression-free at 6-months will be compared using a one-sided test of binomial proportions (equivalent to a Pearson's chi-squared test). If the assumptions of the Pearson's chi-squared test are not met, Barnard's exact unconditional test of equality will be used, as implemented in StatXact.

Patients unevaluable for progression at 6-months due to a non-progression related event will be excluded from analysis.

Statistical comparison of progression-free survival between the two treatment arms will be performed using a log-rank test, with estimation of the hazards ratio using a Cox proportional hazards model. A sensitivity analysis will include patients with an outcome of death due to another cause (other than progressive disease), which will be considered a competing event for progression. Analysis will be performed using the Fine and Gray (1999) approach.

Secondary outcome 1: Toxicity

All adverse events (AE) occurring on or after C1/D1 will be summarized by body systems and per grade according to NCI-CTCAE Version 4. Additionally, all serious adverse events (SAE) and events of clinical interest (ECI) will be listed separately and tabulated. ECIs for this trial include an overdose of pembrolizumab and an elevated AST or ALT lab value, as defined in section 6.2.3.2 of the protocol. All patients who receive any amount of trial treatment will be included in the analysis. The proportion of patients in each arm with toxicity will be compared using a chi-squared test or Barnard's exact unconditional test of equality as outlined above.

Secondary outcome 2: Overall survival

Overall survival will be calculated for each arm using a Kaplan-Meier estimate. Statistical comparison of overall survival between the two treatment arms will be performed using a log-rank test, with estimation of the hazards ratio using a Cox proportional hazards model. Patients with an outcome of death due to another cause (other than progressive disease) will be considered a competing event for death. Analysis will be performed using the Fine and Gray (1999) approach.

Exploratory outcome 1: RECIST 1.1 versus iRECIST

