Comparison of the proportion of patients who are progression-free at 6 months using iRECIST will be performed using the same method as for the primary endpoint of RECIST 1.1. McNemar's test will be used to estimate the concordance between RECIST 1.1 and iRECIST.

7.2 MEASURES TO ADJUST FOR MULTIPLICITY, CONFOUNDERS, HETEROGENEITY, ETC.

Since all primary and secondary endpoints are pre-specified, there will be no adjustment for multiple comparisons. In the context of a randomized clinical trial, the two treatment arms are expected to be balanced with regard to potential confounders, therefore, adjustment is generally not necessary.

References:

Fine, J. P., and R. J. Gray. 1999. A proportional hazards model for the subdistribution of a competing risk. *Journal of the American Statistical Association* 94: 496–509.

Proposed Tables

Table 1. Characteristics of patients at baseline

Characteristic	Pembrolizumab n = x	Pembrolizumab + Paricalcitol n = x	Total n = x
Age, y			
Median			
Range			
Sex, n (%)			
Female			
Male			
Race/ethnicity, n (%)			
Asian			
Black			
White			
Hispanic			
Other			
Study site, n (%)			
HonorHealth Research Institute			
City of Hope			
Atlantic Health System			
Baylor Scott and White Research Institute			
University of Kansas Medical Center			
Medical College of Wisconsin			
Pancreatic tumor location, n (%)			
Head			
Body			
Tail			
Unknown			
Site of metastatic disease, n (%)			
Liver			
Lung			
Peritoneum			
No. of metastatic sites, n (%)			
1			
2			
3			
>3			

Carbohydrate antigen (CA) 19-9			
Median, U/mL			
Range, U/mL			
Normal (0-35 U/mL), n (%)			
ULN to <59x ULN, n (%)			
≥59x ULN, n (%)			
Previous therapy, n (%)			
Radiation therapy			
Chemotherapy			
Whipple procedure			
Biliary stent			

Figure 1. (A) Progression-free survival by investigator-assessment, (B) Progression-free survival by independent assessment, (C) Overall survival

Table 2. Progression-free survival and overall survival in the intention-to-treat population

Efficacy variable	Pembrolizumab n = x	Pembrolizumab + Paricalcitol n = x	Hazard ratio or Response-rate ratio (95% CI)	P value
Progression-free survival by investigator-assessment				
RECIST 1.1				
Rate of progression-free survival, % (95% CI)				
6 mo				
12 mo				
Median progression-free survival, mo (95% CI)				
Progression-free survival by independent assessment				

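### SAP 6 judges evaluability time point by time point and never says how 6-month status is derived from the scan history; read literally, it can drop patients whose status the scans settle

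*SAP*

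**What the plan says.** SAP section 6 is the whole of the plan's text on missing values and data conventions: "Patients with missing values at a particular time point will be unevaluable at that time point. Missing data will not be imputed".

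SAP 7.1 then says, for the primary comparison of proportions: "Patients unevaluable for progression at 6-months due to a non-progression related event will be excluded from analysis".

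Protocol 8.3.4 sets a different analysis set: "All patients that receive trial treatment will be included in the analysis". Table 2 in the SAP's proposed tables is titled "Progression-free survival and overall survival in the intention-to-treat population".

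Both documents fix the primary time point at day 180 from cycle 1 day 1 (Protocol 8.3.4, SAP 5). Protocol 6.1.2.6 schedules tumour imaging every 9 ± 1 weeks. Appendix 5 of the protocol measures RECIST 1.1 progression in target lesions by "taking as references the smallest sum of diameters recorded on study", and counts any new lesion as progression.

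Neither document gives an assessment window around day 180 or a rule for reading 6-month status from scans taken before or after that day.

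**The concern.** Being progression-free at 6 months is a statement about the patient's whole history up to that point, not a measurement at one visit. Progression before the 6-month scan already fixes the outcome. If the 6-month scan is missed and the next one shows no progression against the on-study nadir, that is strong evidence that the patient was progression-free at 6 months. A per-time-point rule ignores both facts. It labels the second patient unevaluable, and 7.1 may then remove that patient from the powered comparison.

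The trial has 12 patients per arm, no dropout allowance, and no replacement of patients who discontinue after starting treatment (Protocol 4.9). One patient can decide the result. A rule applied after unblinding to settle who counts as evaluable would be open to challenge in either direction.

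**Working it through.** **1. The plan's own figure.** Inputs from Protocol 8.2 and the synopsis: 12 per arm, progression-free proportions 1/12 and 7/12, one-sided alpha 0.05, Pearson test by binomial enumeration. For a control and b combination successes, with p the pooled proportion,

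z = (b/n₂ − a/n₁) / √[p(1 − p)(1/n₁ + 1/n₂)], reject if z ≥ 1.645.

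Summing the binomial probabilities of all 13 × 13 outcomes that reject gives power 90.1%. The stated 90% is reproduced. The score method gives 88.8%, against 89% stated.

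**2. Scan days against day 180.** The k-th scan is due on day 63k: 63, 126 and 189. With ± 7 days around the calendar date, the third scan falls on days 182 to 196, always after day 180. If the window accumulates from scan to scan, the range is days 168 to 210. For most patients there is no scan on day 180 itself, so status has to come from neighbouring scans.

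**3. Who is at risk when the third scan is missed.** Patients with documented progression by day 126 keep a known status. The rest are those clean at day 126. Assume a constant hazard and progression-free proportions p = 1/12 and 7/12 at day 189. Then S(126) = p^(126/189) = p^(2/3).

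| Arm | Clean at day 126 | Progression-free at day 189 | Progress between the two | Share of those clean at day 126 |
|---|---|---|---|---|
| Control | 19.1% | 8.3% | 10.7% | 56% |
| Combination | 69.8% | 58.3% | 11.5% | 16% |

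So a missed scan removes late progressors as well as non-progressors.

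**4. Effect on the primary test.** Let each patient clean at day 126 miss the third scan with probability m and be excluded. The expected progression-free proportion among those analysed is p(1 − m) / (1 − m·p^(2/3)). For the combination arm at m = 0.10: 0.5833 × 0.90 / (1 − 0.10 × 0.698) = 0.564. Power comes from enumerating successes, exclusions and failures in each arm with the test in step 1.

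| Assumed m | Combination rate | Power |
|---|---|---|
| 0 | 58.3% | 90.1% |
| 5% | 57.4% | 88.1% |
| 10% | 56.4% | 86.9% |
| 20% | 54.2% | 84.6% |

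**5. One patient.** With 1/12 against 5/12, z = 1.886 and one-sided p = 0.030. Remove one progression-free combination patient (4/11): z = 1.628 and p = 0.052. A score-ordered unconditional exact test moves from 0.036 to 0.065.

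**6. A partial repair is not neutral.** Suppose a later clean scan rescues a patient but a missed scan followed by progression still leads to exclusion. The combination rate becomes p / [1 − m(p^(2/3) − p)] = 58.7%, 59.0% or 59.7% for m = 5%, 10% or 20%, above the true 58.3%. Retention then depends on the later result.

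**The case against.** The strongest reply is that classifying day 180 from a later scan is derivation from observed data, so the sentence "Missing data will not be imputed" does not forbid it. That is right about imputation. But "Patients with missing values at a particular time point will be unevaluable at that time point" is a separate rule, and it is the one that creates the problem.

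Second, the exclusion in 7.1 is limited to non-progression related events, and a skipped or unreadable scan is not clearly one. This stands, and it narrows the point. A patient outside that qualifier is still unevaluable under section 6 and has no assigned status, so cannot enter a binary test.

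Third, a literal day-180 reading would make nearly every non-progressor unevaluable, so it cannot be what was intended. Probably so, which is a reason to write the intended rule down. Later scans also still feed the log-rank and Cox analyses of progression-free survival, but those do not replace the powered comparison of proportions.

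Three stronger readings are tempting and are not supported:

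- A reader might infer that the plan orders known outcomes to be discarded. It does not say so; it fails to say how they are used.
- A reader might infer that only non-progressors can be removed. Step 3 shows that late progressors are removed too.
- A reader might infer that deaths or adverse events with incomplete dates are lost, since survival contact is by telephone ("During the Survival Follow-up Phase the patient should be contacted by telephone 90 ± 5 days from EOT"). The documents do not mention partial dates, and the contact interval governs when a death is learned, not how precisely it is dated. A partial-date convention is a drafting detail.

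**Conclusion.** The concern holds as a gap in the derivation of the primary endpoint that should be closed before unblinding. Sections 6 and 7.1 of the SAP, read literally, can drop patients whose 6-month status the scan history settles, which conflicts with Protocol 8.3.4 and with the title of SAP Table 2. The net effect is a lower progression-free rate and a loss of roughly 2, 3 or 5.5 points of power at missed-scan rates of 5%, 10% or 20%.

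Those sizes rest on three assumptions: the missed-scan rates, which the documents do not give; a constant hazard; and exclusion of every patient clean at day 126 who misses the third scan. If 7.1's qualifier is applied narrowly, fewer patients are excluded. The finding that one patient can move the p-value across 0.05 does not depend on the missed-scan rate, but it is an illustrative data set, not a forecast.

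**What to change.** For the primary endpoint, replace the per-time-point rule in SAP 6 and the exclusion sentence in SAP 7.1 with a derivation from the whole scan history:

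1. Define a 6-month assessment window that covers the week-27 scan with its allowed deviation.
2. Progression documented at or before that assessment counts as progressed.
3. A scan without RECIST 1.1 progression at or after that assessment, with no earlier progression, counts as progression-free.
4. A missed 6-month scan followed by progression at the next scan counts as progressed in both arms, with a sensitivity analysis the other way, so that retention does not depend on the later result.
5. All other treated patients stay in the primary test, as Protocol 8.3.4 requires, with best- and worst-case results for those whose status is still unknown.

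The cost is a few lines of SAP text and programming on data already collected. One small downside remains: a later clean scan cannot rule out a transient increase at the missed scan, which would have counted as progression under RECIST 1.1. The SAP should say so.

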7 STATISTICAL METHODOLOGY

7.1 STATISTICAL PROCEDURES

Primary outcome: Progression-free survival

The proportion of patients in each arm who are progression-free at 6-months will be compared using a one-sided test of binomial proportions (equivalent to a Pearson's chi-squared test). If the assumptions of the Pearson's chi-squared test are not met, Barnard's exact unconditional test of equality will be used, as implemented in StatXact.

Patients unevaluable for progression at 6-months due to a non-progression related event will be excluded from analysis.

Statistical comparison of progression-free survival between the two treatment arms will be performed using a log-rank test, with estimation of the hazards ratio using a Cox proportional hazards model. A sensitivity analysis will include patients with an outcome of death due to another cause (other than progressive disease), which will be considered a competing event for progression. Analysis will be performed using the Fine and Gray (1999) approach.

Secondary outcome 1: Toxicity

All adverse events (AE) occurring on or after C1/D1 will be summarized by body systems and per grade according to NCI-CTCAE Version 4. Additionally, all serious adverse events (SAE) and events of clinical interest (ECI) will be listed separately and tabulated. ECIs for this trial include an overdose of pembrolizumab and an elevated AST or ALT lab value, as defined in section 6.2.3.2 of the protocol. All patients who receive any amount of trial treatment will be included in the analysis. The proportion of patients in each arm with toxicity will be compared using a chi-squared test or Barnard's exact unconditional test of equality as outlined above.

Secondary outcome 2: Overall survival

Overall survival will be calculated for each arm using a Kaplan-Meier estimate. Statistical comparison of overall survival between the two treatment arms will be performed using a log-rank test, with estimation of the hazards ratio using a Cox proportional hazards model. Patients with an outcome of death due to another cause (other than progressive disease) will be considered a competing event for death. Analysis will be performed using the Fine and Gray (1999) approach.

Exploratory outcome 1: RECIST 1.1 versus iRECIST

Comparison of the proportion of patients who are progression-free at 6 months using iRECIST will be performed using the same method as for the primary endpoint of RECIST 1.1. McNemar's test will be used to estimate the concordance between RECIST 1.1 and iRECIST.

7.2 MEASURES TO ADJUST FOR MULTIPLICITY, CONFOUNDERS, HETEROGENEITY, ETC.

Since all primary and secondary endpoints are pre-specified, there will be no adjustment for multiple comparisons. In the context of a randomized clinical trial, the two treatment arms are expected to be balanced with regard to potential confounders, therefore, adjustment is generally not necessary.

References:

Fine, J. P., and R. J. Gray. 1999. A proportional hazards model for the subdistribution of a competing risk. *Journal of the American Statistical Association* 94: 496–509.

Proposed Tables

Table 1. Characteristics of patients at baseline

Characteristic	Pembrolizumab n = x	Pembrolizumab + Paricalcitol n = x	Total n = x
Age, y			
Median			
Range			
Sex, n (%)			
Female			
Male			
Race/ethnicity, n (%)			
Asian			
Black			
White			
Hispanic			
Other			
Study site, n (%)			
HonorHealth Research Institute			
City of Hope			
Atlantic Health System			
Baylor Scott and White Research Institute			
University of Kansas Medical Center			
Medical College of Wisconsin			
Pancreatic tumor location, n (%)			
Head			
Body			
Tail			
Unknown			
Site of metastatic disease, n (%)			
Liver			
Lung			
Peritoneum			
No. of metastatic sites, n (%)			
1			
2			
3			
>3			

Carbohydrate antigen (CA) 19-9			
Median, U/mL			
Range, U/mL			
Normal (0-35 U/mL), n (%)			
ULN to <59x ULN, n (%)			
≥59x ULN, n (%)			
Previous therapy, n (%)			
Radiation therapy			
Chemotherapy			
Whipple procedure			
Biliary stent			

Figure 1. (A) Progression-free survival by investigator-assessment, (B) Progression-free survival by independent assessment, (C) Overall survival

Table 2. Progression-free survival and overall survival in the intention-to-treat population

Efficacy variable	Pembrolizumab n = x	Pembrolizumab + Paricalcitol n = x	Hazard ratio or Response-rate ratio (95% CI)	P value
Progression-free survival by investigator-assessment				
RECIST 1.1				
Rate of progression-free survival, % (95% CI)				
6 mo				
12 mo				
Median progression-free survival, mo (95% CI)				
Progression-free survival by independent assessment				
Rate of progression-free survival, % (95% CI)				
6 mo				
12 mo				
Median progression-free survival, mo (95% CI)				
Overall survival				
Median overall survival, mo (95% CI)				
Survival rate, % (95% CI)				
6 mo				
12 mo				

Table 3. Common adverse events of grade 3 or higher

Event	Pembrolizumab n = x	Pembrolizumab + Paricalcitol n = x	P value
Adverse event leading to death, no. (%)			
Serious Adverse Events			
Anemia			
Cataract			
Nausea			
Abdominal pain			
Diarrhea			
Vomiting			
Bloating			
Constipation			
Fatigue			
Gait disturbance			
Urinary tract infection			
AST increased			
ALT increased			
Alkaline phosphatase increased			
Arthralgia			
Pain in extremity			
Back pain			
Hypertension			

Note: these were the most common events on the Nov 2019 DSMB report (> 10% of patients)

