3.4 Primary Endpoints

The percent of patients with radiographic disease progression according to RECIST 1.1 at 6 months.

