8.2 Sample Size Considerations

The primary endpoint is the percentage of patients progressing at 6 months. Based on a contemporary control of no maintenance after best response to prior chemotherapy⁸, the control arm with pembrolizumab alone is expected to have only 8% of patients with no progression at 6 months. To be of clinical interest, at least 58% of patients must be progression-free at 6 months on the pembrolizumab plus paricalcitol arm. A sample size of 12 patients per arm will provide 90% statistical power to detect this difference assuming a one-sided alpha level of 0.05. A one-sided test was selected as we are only interested in the combination if it decreases the percentage of patients progressing at 6 months. This sample size estimate was obtained using binomial enumeration of all possible outcomes to compare two independent binomial proportions (Pearson's chi-squared test) using PASS 15.¹⁸ A statistical concern is that the Pearson chi-squared test does not guarantee the alpha level. We confirmed that we have adequate statistical power using the Miettinen & Nurminen¹⁹ exact likelihood score method (89% power) using Pass 15.

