5 ENDPOINTS AND COVARIATES

Primary endpoint: Percent of patients with radiographic disease progression according to RECIST 1.1 at 6 months, defined as 180 days from initial treatment (C1/D1).

Secondary endpoints:

- (1) Incidence of toxicities
From initial treatment to end-of-treatment
- (2) Overall survival
Time from initial treatment to death

Exploratory endpoints:

- (1) Disease progression according to RECIST 1.1 versus iRECIST criteria
Percent of patients with radiographic disease progression at 6 months

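### The SAP drops patients with a non-progression exit from the primary 6-month test; the protocol keeps all treated patients but does not say how an unassessed one counts

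*SAP*

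**What the plan says.** The endpoint is worded as radiographic. Protocol 3.4 has "The percent of patients with radiographic disease progression according to RECIST 1.1 at 6 months", and SAP 5 has "Percent of patients with radiographic disease progression according to RECIST 1.1 at 6 months, defined as 180 days from initial treatment".

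On who enters the test, the documents differ. Protocol 8.3.4: "All patients that receive trial treatment will be included in the analysis to determine the percentage of patients progressing by RECIST 1.1 criteria". SAP 7.1, directly after naming the same one-sided test of proportions with Barnard's test as fallback: "Patients unevaluable for progression at 6-months due to a non-progression related event will be excluded from analysis". SAP 6 adds "Patients with missing values at a particular time point will be unevaluable at that time point" and rules out imputation.

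Two other SAP items touch on this. After the log-rank and Cox comparison, SAP 7.1 says "A sensitivity analysis will include patients with an outcome of death due to another cause (other than progressive disease", handled as a competing event by the Fine and Gray method. Proposed Table 2, which has a 6-month rate row, is titled "Progression-free survival and overall survival in the intention-to-treat population".

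**The concern.** The primary analysis is not uniquely defined. A treated patient who leaves for a reason other than progression and has no 6-month status is removed under the SAP and kept under the protocol. If kept, that patient can still be counted in two ways. Read literally, an endpoint of radiographic progression leaves someone without a PD scan as not progressed. A progression-free proportion, which is what both documents say is tested, suggests that such a patient has not been shown to be progression-free.

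The exclusion also selects on an event after randomisation that treatment may influence. If the dropped patients are failures, the arm with more of them gains; if they were progression-free, it loses. If the rule is chosen after unblinding, the test is no longer pre-specified.

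**Working it through.** **Who is affected.** SAP 7.1 reaches only exits due to a non-progression related event, a term it does not define. Clearly inside are non-cancer deaths, and toxicity stops, withdrawals or new therapy that leave no 6-month status. A patient with documented PD before leaving still counts. A cancer death without a PD scan is unclear, because the same section sets deaths from other causes apart. So is symptomatic deterioration, which the note to Table S1 in Appendix 5 says is not objective PD.

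How many patients lack a status is also uncertain. Protocol 4.8 asks for disease-status follow-up until progression, 6.1.2.6 for scans until the later of discontinuation or progression, and 6.1.7.3 for an end-of-treatment scan. But 4.9 describes the follow-up as by phone, and 6.1.1.5.3 moves patients on new therapy to survival follow-up.

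**Does anything else restore the denominator?** The Fine and Gray analysis brings back only deaths not due to PD, and only in the time-to-event comparison. Nothing links Table 2 to the test of proportions. Appendix 5 item 1.2 defines evaluability for response, not for 6-month progression.

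**The plan's own figure.** Inputs: 12 per arm, progression-free rates 1/12 and 7/12, one-sided alpha 0.05 (protocol synopsis and 8.2). Power is the sum of Bin(a; 12, 1/12) × Bin(b; 12, 7/12) over all tables (a, b) that the test rejects. For Pearson this gives 90.1%, matching "A sample size of 12 patients per arm will provide 90% statistical power to detect this difference". The Miettinen and Nurminen check gives 88.8% to 89.0% against the stated 89%. Barnard gives 85.1%. All of these assume 12 evaluable patients per arm.

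**Borderline tables.** Pearson: z = (b/m − a/n) / √[p(1−p)(1/n + 1/m)], with p = (a+b)/(n+m). Barnard: the probability of a z at least as large, maximised over the common rate.

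With control 1/12 and, in the combination arm, 4 progression-free and 3 exits:

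- Excluded, 4/9: p = 5/21 = 0.238; z = 0.361/0.188 = 1.92; one-sided p = 0.027.
- Exits as failures, 4/12: p = 5/24 = 0.208; z = 0.250/0.166 = 1.51; one-sided p = 0.066.

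One-sided p, Barnard / Pearson, control 1/12, 4 shown progression-free:

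| Exits in combination arm | Excluded (SAP) | Kept as failures | Kept as not progressed |
|---|---|---|---|
| 1 | 4/11: 0.064 / 0.052 | 4/12: 0.081 / 0.066 | 5/12: 0.036 / 0.030 |
| 2 | 4/10: 0.0499 / 0.039 | 4/12: 0.081 / 0.066 | 6/12: 0.014 / 0.012 |
| 3 | 4/9: 0.037 / 0.027 | 4/12: 0.081 / 0.066 | 7/12: 0.0051 / 0.0047 |

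Comparing exclusion with failures, one exit reverses nothing, two do so by a hair under Barnard, and three do so clearly. The last column shows that the protocol's denominator alone does not settle the verdict.

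The documents do not say when the chi-squared assumptions fail. By the usual criterion of expected counts of at least 5, they fail here (12 × 5/24 = 2.5), so Barnard is the likely test. Under Barnard, one patient can be enough, in either direction, when the exit counts as a failure:

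- Exit in the combination arm: 2/12 v 6/12 is 0.053; excluded, 2/12 v 6/11 is 0.040.
- Exit in the control arm: 1/12 v 5/12 is 0.036; excluded, 1/11 v 5/12 is 0.056.

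**At the planned effect.** 1/12 v 7/12 gives 0.0051 / 0.0047. With two combination failures dropped, 7/10 gives 0.0017 / 0.0014. With two successes dropped, 5/10 gives 0.018 / 0.014. No reversal.

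**How often.** At the design rates, if each patient independently has a 5%, 10% or 20% chance of being unevaluable, exclusion and counting as failures give different Pearson verdicts in 2.4%, 4.3% and 7.4% of trials.

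**The case against.** The strongest reply is that the effect is small and rests on chosen tables. Planned follow-up and scans should give many toxicity stops a status. Exit rates are assumed. The two-exit example turns on 0.0499, and one exit in that setting changes nothing. The SAP also plans a log-rank and Cox analysis, a competing-risk analysis and an intention-to-treat table, so a distorted binomial result would not stand alone. Finally, counting deaths and unassessed patients as failures turns a radiographic endpoint into something closer to a progression-free survival composite, which the documents do not establish as correct.

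Most of this stands as a limit on size. It does not remove the contradiction: the other analyses do not repair the primary test, and the three-exit and single-patient examples do not depend on 0.0499. The point about the composite is fair, so the counting rule below is offered as a convention.

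A reader might infer that everyone who dies without documented PD is dropped. The SAP wording does not support that, since a cancer death is arguably a progression-related event. A reader might also infer that exclusion inflates the type I error. At the design control rate of 1/12, Barnard stays at 3.3% even with assumed exits of 5% v 25%, all failures. Pearson reaches 6.5% there, but with 10% exits in both arms it is 2.9%.

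**Conclusion.** The concern holds in a limited form and should be fixed. SAP 7.1 and protocol 8.3.4 prescribe different denominators for the primary test, the SAP's excluding event is undefined, and the protocol has no counting rule for a treated patient without a 6-month status. Near the significance boundary this can decide the verdict, with three exits in one arm or, under Barnard, sometimes with a single patient, and in either direction.

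It does not follow that the sample size is wrong or that a result at the planned effect is fragile: the 90% reproduces, and 7/12 v 1/12 survives two exclusions from the combination arm. The size rests on assumed exit numbers, on independent exits in the disagreement rates, and on Barnard being the test applied.

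**What to change.** Before unblinding:

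- In SAP 6 and 7.1, use the protocol's all-treated denominator for the primary 6-month test.
- State one counting rule for treated patients without a 6-month radiographic status. Suggested: they are not shown to be progression-free, and any death before 6 months counts as not progression-free. Say how new anticancer therapy and symptomatic deterioration are classified.
- Mark the rule as a convention that clarifies the radiographic endpoint, and align protocol 3.4 and 8.3.4 with it.
- Report the evaluable-only analysis and the best-case and worst-case counts as sensitivity analyses (in the three-exit example, 7/12 and 4/12).
- Say which population the 6-month rate in Table 2 uses.

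The cost is text in both documents, with no new patients or data. Observed percentages may fall (4/9 = 44% becomes 4/12 = 33%), and missing assessments count against the arm that has more of them. Power is slightly lower than under exclusion. At the design rates, Barnard / Pearson, it is 80% / 85% against 81.5% / 86% with 10% random loss in both arms, and 75% / 78.5% against 76% / 82% with 20%.
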